# 6. BASELINE, EXPOSURE, AND DISPOSITION VARIABLES AND ANALYSES

Appendix A provides a list of data displays and sample data displays.

# 6.1. Baseline and Demographics, Physical Characteristics, and Disease History

## 6.1.1. Demographics

The following demographics will be summarized for the Part 1 FAS population by dose level and for the Part 2 FAS population by tumor type: age, sex, race, ethnicity, and ECOG performance status.

## 6.1.2. Baseline Disease Characteristics and Disease History

For each type of tumor, primary tumor histology, date of initial diagnosis, stage at initial diagnosis, current stage of disease, current site of disease, and will be summarized for all subjects in the Part 1 FAS population by dose level and Part 2 FAS population by tumor type.

## 6.1.3. Prior Therapy

Number of prior systemic cancer therapy regimens will be summarized for all subjects in the Part 1 FAS population by dose level and Part 2 FAS population by tumor type. Regimen name, component drugs, start and stop date, purpose of the regimen, best response, reason for discontinuation, and date of relapse/progression will be listed by total number and by number of prior systematic cancer therapies taken for both advanced and metastatic disease.

Number of subjects who received prior radiation will be summarized for the FAS population. Radiotherapy type, body site, start and stop date, total dose, and best response will be listed.

Number of subjects who had prior surgery or surgical procedure for the malignancies under study will be summarized for the FAS population. Date and description of the surgery/procedure will be listed.

Number of subjects with prior immunotherapy and prior anti–PD-1/PD-L1 therapy will be summarized for the Part 1 FAS population by dose level and the Part 2 FAS population by tumor type. Prior immunotherapy type, start and stop date, total dose, and best response will be listed.

## 6.1.4. Medical History

For subjects in the Part 1 FAS population by dose level and Part 2 FAS population by tumor type, medical history will be summarized by assigned treatment group. This summation will include the number and percentage of subjects with significant medical history for each body system/organ class as documented on the CRF.

## **6.2.** Disposition of Subjects

The number and percentage of subjects who were enrolled, treated, completed the study, discontinued study treatment with a primary reason for discontinuation, and discontinued from the study with a primary reason for withdrawal will be summarized for the subjects in the Part 1 FAS population by dose level and Part 2 FAS population by tumor type. The number of subjects enrolled by site will also be provided by treatment group.

#### 6.3. Protocol Deviations and Violations

Protocol deviations and violations recorded on the CRF will be presented in the subject data listings.

## 6.4. Exposure

For subjects in the FAS population, exposure to INCAGN01876 will be summarized descriptively as the following:

- Total number of infusions: Total number of infusions per subject by the time of date cutoff will be the total number of infusions per subject with a nonzero dose of INCAGN01876.
- **Dose administered per cycle:** The actual dose administered in (mg/kg) per cycle.
- Total dose administered in mg/kg: The total actual dose administered (in mg/kg) across cycles for each subject will be determined according to the following calculation:

For an infusion i, let  $C_i$  be the concentration (in mg/mL) of INCAGN01876 and  $V_i$  be the total volume administered (in mL) reported on the INCAGN01876 dosing CRF; let W be the subject's baseline weight (in kg), and N be the total number of infusions

Total dose administered (in mg/kg) = 
$$\sum_{i=1}^{N} \frac{c_i \times v_i}{w}$$

- Average dose in mg/kg: The average dose (in mg/kg) will be the total dose administered (in mg/kg) divided by the total number of infusions.
- Total dose administered in mg: Total actual dose administered (in mg) across cycles for each subject will be determined according to the following calculation: For an infusion i, let  $C_i$ ,  $V_i$ , and N be defined as above

Total dose administered (in mg) = 
$$\sum_{i=1}^{N} C_i \times V_i$$

• Average dose in mg: The average dose (in mg) will be the total dose administered (in mg) divided by the total number of infusions.

## 6.5. Prior and Concomitant Medication

Prior medications and concomitant medications will be coded using the WHO Drug Dictionary and summarized by WHO drug class and WHO drug term by dose level in the Part 1 FAS population and by tumor type in the Part 2 FAS population. Results will be summarized as number and percentage of subjects with prior and concomitant medications by PT and WHO drug class.

### 7. EFFICACY

Sample data displays are provided in Appendix A.

#### 7.1. General Considerations

Efficacy endpoints of this study are secondary and include ORR, DOR, duration of disease control, and PFS by investigator assessment based on RECIST v1.1 and mRECIST v1.1.

# 7.2. Efficacy Hypotheses

Each Simon 2-stage design will test the null hypothesis that the true ORR is less than or equal to the clinically insignificant response rate 5% against the alternative hypothesis that the true ORR is equal to the target ORR of 25%.

# 7.3. Analysis of the Primary Efficacy Parameter

Not applicable.

## 7.4. Analysis of the Secondary Efficacy Parameter

### 7.4.1. Response Criteria

Overall disease status will be categorized using RECIST v1.1 and mRECIST v1.1. Subjects will have their overall response evaluated as CR, PR, SD, PD, or NE at each postbaseline radiological assessment based on changes in target lesions, nontarget lesions, and appearance of new lesions.

### 7.4.2. Objective Response Rates and Best Overall Response

A subject is defined as an objective responder if the subject has an overall response of CR or PR at any postbaseline visit before first PD. Objective responders will be assessed based on both RECIST v1.1 and mRECIST v1.1.

Objective response rate is defined as the proportion of subjects with objective responses. Objective response rate will be estimated with 95% CIs overall by cohort-specific tumor type. Confidence intervals will be calculated based on the method for Simon 2-stage CIs of response rates outlined in Koyama and Chen (Koyama and Chen 2008). Subjects who do not have sufficient baseline or on-study response assessment information to be adequately assessed for response status will be included in the denominators in the calculation of ORR.

## 7.4.2.1. Objective Response Rate by RECIST v1.1

Under RECIST v1.1, the best overall response is determined on subject level using the highest overall response achieved postbaseline before and including the first PD, in the order of CR, PR, SD, PD, and NE. Responses of CR, PR, or SD after the first assessment of PD will not be considered. In the case of SD, measurements must meet the SD criteria at least after the date of first dose at a minimum of 49 (56-57) days. Subjects who fail to meet this criterion will have best overall response of PD if the next available assessment indicated PD or NE if there is no additional assessment available.

For subjects with measurable disease at baseline, the RECIST v1.1 assessment criteria presented in Table 3 can be used to determine the overall disease status at a given timepoint based on the target lesion, nontarget lesion, and new lesion assessment.

Table 3: RECIST Evaluation Criteria for Overall Response: Measurable Disease at Baseline

| Target Lesions    | Nontarget Lesions | New Lesions | Overall Response |
|-------------------|-------------------|-------------|------------------|
| CR                | CR                | No          | CR               |
| CR                | Non-CR/non-PD     | No          | PR               |
| CR                | NE                | No          | PR               |
| PR                | Non-PD or NE      | No          | PR               |
| SD                | Non-PD or NE      | No          | SD               |
| Not all evaluated | Non-PD            | No          | NE               |
| PD                | Any               | Yes or No   | PD               |
| Any               | PD                | Yes or No   | PD               |
| Any               | Any               | Yes         | PD               |

## 7.4.2.2. Objective Response Rate by mRECIST v1.1

The mRECIST v1.1 instrument was adapted from RECIST v1.1 to include criteria that accounts for new lesions that can occur in immuno-oncology subjects before the occurrence of an SD, PR, or CR. Under mRECIST v1.1, if radiologic imaging shows PD, tumor assessment should be repeated at a minimum of 4 weeks but not more than 6 weeks later to confirm the progression. If there is no second PD tumor assessment in the 4- to 6-week follow-up time, the PD will be defined as unconfirmed. Table 4 lists the scenarios that can occur after an unconfirmed PD in at least 4 weeks and no more than 6 weeks and provides rules for determining whether or not the unconfirmed PD will be counted as an event in the corresponding scenario.

Table 4: Rules for Determining PD Event Status After an Unconfirmed PD

| Event Occurring After Unconfirmed PD in the Confirmation Window (4-6 weeks) | PD Event Status   |
|---|---|
| Subject had EOS/EOT or started new anticancer therapy.                      | PD will be confirmed as a PD.   |
| Subject had a confirmed PD.   | PD will be confirmed as a PD.   |
| Subject had an CR, PR, SD, or NE.   | PD will not be considered as a PD and counted as corresponding CR, PR, SD, or NE for the second timepoint only. |

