- ^j On-study imaging will be performed at Week 8 and then every 8 weeks (± 7 days) for the first 12 months and then every 12 weeks (± 7 days) thereafter. Imaging should follow calendar days and should NOT be adjusted for delays in cycle starts. If imaging shows disease progression, then another imaging assessment should be performed at a minimum of 4 weeks, but no later than 6 weeks later to confirm progression per mRECIST.
- ^k If scan was obtained within 4 weeks prior to the date of discontinuation, then a scan at treatment discontinuation (EOT) is not mandatory. For subjects who discontinue study therapy without confirmed disease progression, a radiologic evaluation should be repeated at the time of treatment discontinuation (ie, date of discontinuation ± 4 week window). For subjects who discontinue treatment for reasons other than disease progression, every effort should be made to continue monitoring their disease status every 8 weeks (± 7 days) by radiographic imaging until 1) start of new antineoplastic therapy, 2) documented disease progression, 3) death, or 4) the end of the study, whichever occurs first.

Table 8: Schedule of Laboratory Assessments

Visit Day (Range)	Protocol Section	Screening	Treatment				Post-Treatment		
			C1 and C2		Odd Numbered Cycles (C3, C5, C7, C9, etc)	Even Numbered Cycles (C4, C6, C8, etc)	EOT	Safety Follow-Up Visit 1	Safety Follow-Up Visit 2
			D1	D7	D1	D1			
Evaluation/Window		Day -28 to -1	Predose	± 1 day	± 3 days	± 3 days	± 3 days	30 days (+ 7 days)	60 days (+ 7 days)
Local Laboratory Tests^a									
Comprehensive serum chemistries ^b	7.6.5	X ^c	X	X	X	X	X	X	X
Hematology with differential	7.6.5	X ^c	X	X	X	X	X	X	X
Coagulation panel	7.6.5	X ^c	X	X	X		X	X	X
Urinalysis	7.6.5	X ^c	X	X	X		X		
Endocrine function tests	7.6.5	X ^c	X	X	X		X	X	X
Hepatitis B and C	7.6.5.2	X ^c							
Serum pregnancy test (childbearing females only) ^d	7.6.5.1	X ^c					X		
Urine pregnancy test (childbearing females only) ^e	7.6.5.1				X	X			

^a All safety laboratory assessments will be performed locally.

^b If liver chemistry tests are abnormal (eg, change in grade from baseline), then liver chemistry monitoring should increase to once per week until resolved to baseline. Liver chemistry does not need to be monitored once per week indefinitely for persistent low grade abnormalities. Appropriate liver chemistry monitoring intervals should be discussed with the medical monitor for these circumstances.

[figure not shown]

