### 7.4.8.2. Progression-Free Survival by mRECIST v1.1

Under mRECIST v1.1, PFS is defined as the length of time between the baseline visit (Day 1) and the earlier of death or first overall confirmed assessment of PD (as described in Section 7.4.2.2).

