### 7.4.8.2.1. Confirmation of Progression per mRECIST v1.1

Under mRECIST v1.1, the assessment of PD will be confirmed by a second consecutive assessment at least 4 weeks but no later than 6 weeks apart with the option for continuing treatment while awaiting radiologic confirmation of progression (Table 4).

• If after the first unconfirmed PD, there is an EOT/EOS or a new treatment is started, this unconfirmed PD will be counted as a confirmed PD, and DOR will be defined as the time from the first overall response (CR or PR) to this PD, or death from any cause if occurring sooner than the PD.

- If a second PD occurs after the first unconfirmed PD, the first unconfirmed PD will be counted as a confirmed PD, and DOR will be defined as the time from the first overall response (CR or PR) to the first PD, or death from any cause if occurring sooner than the confirmed PD.
- If a CR, PR, SD, or NE occurs after the first unconfirmed PD, the unconfirmed PD will not be counted as a PD. If there is no further PD assessment, DOR will be censored.

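### SAP Table 4 confirms an mRECIST progression only by an event in weeks 4–6, but the bullets of SAP 7.4.8.2.1 and the shell footnotes set no window, so early stops and late second PDs have no settled status

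*SAP*

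**What the plan says.** **The windowed rule.** SAP 7.4.2.2 reads: "If there is no second PD tumor assessment in the 4- to 6-week follow-up time, the PD will be defined as unconfirmed". The left-hand column of SAP Table 4 is headed "Event Occurring After Unconfirmed PD in the Confirmation Window (4-6 weeks"), so the window applies to each of its three rows:
- row 1, "Subject had EOS/EOT or started new anticancer therapy": the PD is confirmed;
- row 2, a further PD: confirmed;
- row 3, CR, PR, SD or NE: not a PD.

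SAP 7.4.8.2 takes the mRECIST PFS event to be death or the "first overall confirmed assessment of PD (as described in Section 7.4.2.2"). SAP 7.4.4.2 (DOR) and 7.4.5 (duration of disease control) refer to the same section.

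**The rule without a window.** SAP 7.4.8.2.1 opens by requiring PD to be "confirmed by a second consecutive assessment at least 4 weeks but no later than 6 weeks apart" and cites Table 4. Its first bullet deals with a stop that follows an initial PD still lacking confirmation: "there is an EOT/EOS or a new treatment is started, this unconfirmed PD will be counted as a confirmed PD". Its second says "If a second PD occurs after the first unconfirmed PD, the first unconfirmed PD will be counted as a confirmed PD". Neither bullet carries a time limit. The third bullet agrees with row 3 of Table 4. The footnotes of shells 2.2.1 and 2.2.2 count an unconfirmed PD after EOS/EOT or new therapy, again with no time limit.

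**The Protocol.** Table 7, footnote j: "On-study imaging will be performed at Week 8 and then every 8 weeks", with ± 7 days, moving to every 12 weeks after 12 months. It adds a dedicated scan 4 to 6 weeks after a PD. Section 7.7.1 and Table 12 have clinically unstable subjects discontinue at first PD without a required repeat scan. The synopsis (Efficacy Assessments) requires confirmation only where there is no clinical deterioration. Section 7.7.1 also says that when a PD is not confirmed and treatment continues, a later PD with its own 4–6 week confirmation sets the progression date.

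**The concern.** The SAP gives two rules for one event, and two programmers could each follow it and produce different mRECIST PFS and DOR. The subjects on whom the rules differ are not a random subset. They include those who deteriorate clinically and stop at their first PD, and those whose confirmatory scan was missed or late.

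If the first PD is not counted, SAP Table 5 leaves two main outcomes: censoring at the last valid scan, or an event only at a later death. Both replace an event at the first PD scan with something more favourable, so Kaplan-Meier estimates of mRECIST PFS and DOR move upward.

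**Working it through.** The plan states no figure here. The check compares the two rules case by case and then uses date arithmetic to see whether the conflicting cases can be expected. Day 0 is the first PD scan, and the window is days 28–42 (4 × 7 to 6 × 7).

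**1. The rules side by side**

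| Course after first PD | SAP 7.4.2.2 and Table 4, read literally | SAP 7.4.8.2.1 bullets |
|---|---|---|
| Second PD, days 28–42 | PD event | PD event at first PD |
| EOT/EOS or new therapy, days 28–42 | PD event | PD event at first PD |
| EOT/EOS or new therapy before day 28 | No row; not confirmed | PD event at first PD |
| Second PD after day 42 | Unconfirmed; no row | PD event at first PD |
| CR, PR, SD or NE, days 28–42 | Not a PD | Not a PD |

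The rules part in rows 3 and 4.

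**2. Can a regular scan serve as the confirmatory scan?** Inputs: 56 ± 7 days, later 84 ± 7 days (Protocol Table 7, footnote j).
- Counted from the previous scan: 56 − 7 = 49 to 56 + 7 = 63 days, that is 7–9 weeks, always after day 42.
- Counted from fixed calendar dates, as footnote j indicates: 56 − 7 − 7 = 42 to 56 + 7 + 7 = 70 days. Of 15 × 15 = 225 whole-day combinations, one reaches day 42 (first scan 7 days late, next scan 7 days early).
- 12-week scans: 84 − 14 = 70 to 84 + 14 = 98 days; none of 225 falls inside.

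If the dedicated scan is missed, a second PD at the next regular scan therefore almost always lands in row 4.

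**3. When does an immediate stop fall?** Protocol 6.3 places the EOT visit at permanent discontinuation; Protocol Table 7 allows ± 3 days.
- Stop at the PD scan: EOT within about 3 days, before day 28.
- Stop at the next cycle's Day 1, taken as at most one cycle plus 3 days after the scan: 14 + 3 = 17 or 21 + 3 = 24 days, both before day 28. With 28-day cycles, 28 + 3 = 31, which can reach the window.

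A prompt stop therefore normally lands in row 3.

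**The case against.** The strongest reply is that the intention is clear and only an over-literal reading of one column header loses events. The Protocol's mRECIST definition exempts clinical deterioration. Protocol 7.7.1.1.2 and SAP Section 9 tie confirmation to clinically stable subjects. Bullet 1 of SAP 7.4.8.2.1 and the shell footnotes already count a PD followed by a stop. This shows what was probably meant, but SAP Table 4 carries no such exemption, and the PFS, DOR and disease-control definitions all lead to 7.4.2.2.

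Second, the bullets of 7.4.8.2.1 sit under a sentence that repeats the window and could be read as inheriting it. That is possible, and row 2 of Table 4 itself uses the term unconfirmed loosely, for a PD awaiting confirmation. But 7.4.2.2 defines an unconfirmed PD as one with no second PD in weeks 4–6. Under that definition bullet 2 can only refer to a second PD outside the window. The section is inconsistent with itself as well as with Table 4.

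Third, the Protocol does not rely on regular scans. It plans a dedicated 4–6 week scan and permits extra imaging. This stands, and it limits the late-PD problem to missed or late confirmatory scans. It does not help the early stop: the repeat scan is discretionary for unstable subjects, and Protocol Table 7, footnote k makes the EOT scan non-mandatory if one was done in the previous 4 weeks.

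Fourth, efficacy is secondary, SAP 3.3 calls all analyses exploratory, and RECIST v1.1 results are reported alongside without PD confirmation. This limits the consequence but leaves the mRECIST results undefined for these subjects.

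**Conclusion.** The point holds. SAP Table 4 and the bullets of SAP 7.4.8.2.1 give different event status to two foreseeable groups: subjects who stop or start new therapy before week 4, and subjects whose second PD comes after week 6. Under the literal Table 4 rule the error in mRECIST PFS and DOR is upward.

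The size cannot be calculated, because the documents give no rate of missed or late confirmatory scans or of immediate stops. A reader might suppose three affected subjects among 17 and infer a shift of 3/17 = 17.6 percentage points in a landmark PFS rate. The three is not in the documents, so this is an illustration and not an estimate. Nor does every affected subject shift by 7–9 weeks: a death two weeks after the first PD moves the event by two weeks, and a PD at Week 16 may itself be confirmed and become the event under Protocol 7.7.1.

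A reader might also infer that the mRECIST response rate is biased. That does not follow. The status of a late second PD could decide whether a subsequent response counts, but the Protocol synopsis deliberately lets a response after an initial PD count.

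The conclusion rests on reading the Table 4 header as written and on the scan and visit windows in Protocol Table 7.

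**What to change.** State one rule in SAP Table 4, SAP 7.4.8.2.1 and the footnotes of shells 2.2.1 and 2.2.2:
- **Stop, new therapy or death.** Count the first PD as the event, dated at that scan, if EOT/EOS, new anticancer therapy or death follows with no intervening CR, PR or SD, whether or not it falls in weeks 4–6.
- **Second consecutive PD after week 6, no intervening non-PD scan.** Choose one rule and reconcile it with Protocol 7.7.1, which dates progression from a later, separately confirmed PD.
- **PD followed by CR, PR or SD.** Keep row 3 of Table 4 and the third bullet of 7.4.8.2.1. Treatment is capped, so most subjects eventually reach EOT or EOS. Without this condition a pseudoprogression followed by response would be back-dated to a PD. Both places also list NE, so say what happens when an NE scan is followed by a stop.
- **No event in the window.** Add a row.

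The cost is SAP and shell wording, settled before the data are reviewed, with no extra scans and no change to treatment. If the choice for a late second PD departs from Protocol 7.7.1, that departure also has to be reconciled with the Protocol.

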## 7.4.3. Subgroup Analyses of Objective Response Rates

Subgroups will be formed based on the following subject characteristics and baseline variables for those subjects whose data are available.

- PD-L1 expression within tumor type: high versus negative/low
- Prior treatment with an anti–PD-1/PD-L1 therapy within tumor type: Yes/No
- Number of prior therapies for advanced and metastatic disease within tumor type
- Subjects with > 1 postbaseline scan within tumor type
- Tumor-type disease characteristics including the following:
  - Endometrium MSI status (high, low, stable, unknown)
  - Melanoma BRAF mutation status (mutated, wild-type, unknown), PD-L1 status (positive or negative)
  - NSCLC Histology (squamous or nonsquamous), PD-L1 status (positive or negative)
  - RCC MSKCC score (Poor, Intermediate, Good), PD-L1 status (positive or negative)

### 7.4.4. **Duration of Response**

Duration of response will be assessed with RECIST v1.1 and mRECIST v1.1 criteria.

Censoring of DOR will follow the same algorithm as the censoring of PFS. Kaplan-Meier curves for DOR will be presented by cohort-specific tumor types. The KM estimate of median DOR will be presented with its 95% CI. The 95% CI will be calculated using Brookmeyer and Crowley's method (Brookmeyer and Crowley 1982). A swim plot for DOR will be generated under both RECIST v1.1 and mRECIST v1.1 criteria.

### 7.4.4.1. Duration of Response by RECIST v1.1

Under RECIST v1.1, for objective responders, DOR is defined as the time from the first overall response contributing to an objective response (CR or PR) to the earlier of the subject's death from any cause or first assessment of PD.

